# 4.0 PATIENT SELECTION

Each of the criteria in the checklist that follows must be met in order for a patient to be considered eligible for this study. Use the checklist to confirm a patient's eligibility. The checklist must be completed for each patient and must be signed and dated by the treating physician.

Patient's Name	
Medical Record #	
Research Nurse /	
Study Coordinator Signature:	Date
Treating Physician [Print]	
Treating Physician Signature:	Date

#### 4.1 Inclusion Criteria

Patients must meet all of the following inclusion criteria to be eligible for enrollment:

4.1.1 Have a diagnosis of CLL based on peripheral blood flow cytometry and/or bone marrow aspiration and biopsy OR diagnosis of SLL based on lymph node or bone marrow biopsy. Patients with SLL need to have measurable disease (see section 12.2 for definition of measurable disease)

4.1.2 Subject, age  $\geq$  18 years (children are excluded from this study as CLL/SLL being exceptionally rare)

- 4.1.3 Performance Status (ECOG) 0-2 (see appendix A) ECOG PS = \_\_\_\_\_ Date: \_\_\_\_\_
  - \_\_\_\_\_\_ 4.1.4 Patients must have not received any prior treatment for CLL or SLL.

	4.1.6 Adequat	e bone marrow, rena	l, and hepatic function, per local reference
lat	ooratory ranges as fol	lows:	
	4.1.6.1 Absolute	e neutrophil count (A	NC) ≥ 1,500/mm3
	A	ANC=	Date:
	4.1.6.2 Platelet of	$count \ge 100,000/mm$	3
	P	latelets=	Date:
	4.1.6.3 Hemoglo	bin > 10 g/dL	
	Hinde Intensity.	Iemoglobin=	Date:
	4.1.6.4 Serum ci	reatinine $\leq 2.0$ g/dL	or calculated creatinine clearance
	(	$(CrCl) \ge 60mL/min$	Cockcroft-Gault method)
	C	Crcl =	Date:
			Date
	4.1.6.5 AST and	$ALT \le 2.5 \text{ x institu}$	tional upper limit of normal
	(	ULN) NST-	Date
	r A	AST= ALT=	Date:
	4.1.6.6 Bilirubir	n < 2.0  x ULN, unles	s subject has Gilbert's disease
	E	siiiruoin=	Date:
	4.1.6.7 Calcium	<10.1 mg/dL (corre	cted to serum albumin as follows:
	Corrected Calcin	um = (0.8 x (4 - patie))	ent albumin)) + serum Ca
	Corrected calciu	ım= Da	ite:
4.	1.7 Females will be	either postmenopau	sal for at least 1 year or surgically sterile
for	r at least 3 months (	OR Females of child	1-bearing potential must have a negative
pr	egnancy test at scre	ening and agree to	take appropriate precautions to avoid
pro	egnancy (double bar	rier method of birt	h control or abstinence) from screening
tin	ough 5 months arter	the last dose of freat	nent
4.1	1.8 Able to compreh	nend and willing to s	ign an Informed Consent Form (ICF)
4.1	1.9 Subjects must be	e off any steroids 7 c	ays prior to the initiation of treatment.
4.1	1.10 Subjects must be	e off any curcumin,	tumeric, or vitamin D supplements for 14
	days prior to the	initiation of treatme	nt.
4	1.11 Subjects must be	able to take oral me	dications
CASE 5913		20 of 7	4

#### 4.2 Exclusion Criteria

The presence of any of the following will exclude a patient from study enrollment.

- 4.2.1 Presence of malignancy (other than the one treated in this study) which required systemic treatment within the past 3 years
- 4.2.2 Any indication to start treatment for CLL based on NCI-WG criteria (see appendix B)
- \_\_\_\_\_ 4.2.3 Prior therapy for CLL/SLL
- 4.2.4 Subjects who are pregnant or breast-feeding

Pregnant or breastfeeding women are excluded from this study because the safety of curcumin had not been established with pregnancy and is unknown. Because there is an unknown, but potential risk for adverse events in nursing infants secondary to treatment of the mother with curcumin, breastfeeding should be discontinued if the mother is treated with curcumin.

- 4.2.5 Concurrent medical condition which may increase the risk of toxicity, including:
  - \_\_\_\_\_ 4.2.5.1 Hypercalcemia of any cause
  - 4.2.5.2 Untreated hyperparathyroidism
  - 4.2.5.3 Paget's disease of bone
  - \_ 4.2.6 Uncontrolled intercurrent illness including, but not limited to, ongoing active infection, symptomatic congestive heart failure, unstable angina pectoris, cardiac arrhythmia, or psychiatric illness/social situation that would limit compliance with study requirements as judged by treating physician; subjects receiving antibiotics that are under control may be included in the study
- \_\_\_\_\_ 4.2.7 Inability to take oral medications.
- \_\_\_\_\_ 4.2.8 Patients receiving other investigational agent
- 4.2.9 History of allergic reactions attributed to compounds of similar chemical or biologic composition to curcumin or vitamin D or other agents used in this study.
- 4.2.10 Patients on therapeutic anticoagulation, with heparin (or low-molecular weight heparin), warfarin, or a direct thrombin inhibitor as the safety of concurrent administration of curcumin has not been established

4.2.11 HIV-positive patients on combination antiretroviral therapy are ineligible because of the potential for pharmacokinetic interactions with curcumin.

# 4.3 Inclusion of Women and Minorities

Both men and members of all races and ethnic groups are eligible for this trial.

# 5.0 REGISTRATION

All subjects who have been consented are to be registered in the OnCore Database. For those subjects who are consented, but not enrolled, the reason for exclusion must be recorded.

All subjects will be registered through University Hospitals Cleveland Medical Center and will be provided a study number.

# 6.0 TREATMENT PLAN

Patients will take both Curcumin and Vitamin D3 for 6 cycles (cycle = 28 days).

Patients who sustained a partial response (PR) or better can elect to extend therapy for a total of 2 years.

# 6.1 Agent Administration

As both agents are well-tolerated with no expected grade 3-4 toxicities, dose modifications are as outlined in section 7.0. Reported adverse events and potential risks of curcumin and vitamin D3 are described in Section 8.0. No investigational or commercial agents or therapies other than those described below may be administered with the intent to treat the patient's malignancy.

TREATMENT REGIMEN DESCRIPTION				
Agent	Dose	Route	Schedule	Cycle Length
Curcumin	8 grams	РО	daily	
Vitamin D3	10,000 IU	РО	Daily starting on D8 of cycle 1 and on D1 on all subsequent cycles	28 day (continuous treatment)
The patient will be provided a Patient Pill Diary [Appendix C and D] and instructed in its				

use to record each dose of oral medication.

# 6.1.1 Curcumin Administration

Patients will take Curcumin 8 grams/day orally with food continuously. Patients will be provided a Patient Pill Diary (Appendix C and D) and instructed in its use to record each dose of oral medication. Curcumin can be administered with other medications.

# 6.1.2 Vitamin D3 Administration

Patients will take vitamin D3 10,000 IU/day orally with food continuously. For cycle 1, vitamin D3 will start 1 week after curcumin (on D8) only with initiation of treatment and will be given with curcumin continuously there after. Patients will be provided a Patient Pill Diary (Appendix C and D) and instructed in its use to record each dose of oral medication. Vitamin D3 can be administered with other medications..

# 6.2 General Concomitant Medications and Supportive Care Guidelines

Because there is a potential for interaction of curcumin with other concomitantly administered drugs through the cytochrome P450 system, the case report form must capture the concurrent use of all other drugs, over-the-counter medications, or alternative therapies. The Principal Investigator should be alerted if the patient is taking any agent known to affect or with the potential to affect CYP1A2 and CYP2A6 activity (85). Please refer to Appendix E-F for a complete list.

As patients with early stage CLL/SLL are frequently asymptomatic, have no significant cytopenias at baseline, and as both high dose vitamin D3 and curcumin were both well tolerated in clinical trials, we don't expect that study subjects will need supportive care.

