# 6.3 **Duration of Therapy**

In the absence of treatment delays due to adverse events, which are not generally expected, treatment may continue for 6 cycles [or can be extended for a total of 2 years if sustained a partial response (PR) or better] until one of the following criteria applies:

- Disease progression,
- Intercurrent illness that prevents further administration of treatment,
- The investigator considers it, for safety reasons, to be in the best interest of the patient.
- Unacceptable treatment related toxicity, NCI CTC AE version 4.0. Grade 3 or 4 that fails to recover to baseline or < Grade 3 in the absence of treatment within 4 weeks]
- General or specific changes in the patient's condition render the patient unacceptable for further treatment in the judgment of the investigator,
- Patient decision to withdraw from treatment (partial consent) or from the study (full consent),
- Pregnancy during the course of the study for a child-bearing participant
- Death

The date and reason for discontinuation must be documented. Every effort should be made to complete the appropriate assessments.

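### The 4.2.10 bar on therapeutic anticoagulants stops at enrolment: no on-study rule says what to do with curcumin if one is started during treatment

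*Combined protocol and SAP*

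**What the plan says.** **At entry.** Section 4.2.10 excludes patients on therapeutic heparin (including low-molecular-weight heparin), "warfarin, or a direct thrombin inhibitor as the safety of concurrent administration of curcumin has not been established". The section 4.2 list governs enrolment only. The next item, 4.2.11, makes HIV-positive patients on combination antiretrovirals "ineligible because of the potential for pharmacokinetic interactions with curcumin".

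**During treatment.**
- Section 6.1 forbids only other therapies aimed at the malignancy.
- Section 6.1.1, among its dosing instructions, states: "Curcumin can be administered with other medications". Section 6.1.2 says the same of vitamin D3.
- Section 6.2 requires that "the case report form must capture the concurrent use of all other drugs, over-the-counter medications, or alternative therapies". It adds that the Principal Investigator, in its words, "should be alerted if the patient is taking any agent known to affect or with the potential to affect CYP1A2 and CYP2A6 activity", and continues: "Please refer to Appendix E-F for a complete list".
- Section 6.3 lists reasons to stop, including "Intercurrent illness that prevents further administration of treatment" and "The investigator considers it, for safety reasons, to be in the best interest of the patient". A third covers a change in the patient's condition. None names a drug.
- Section 7.0 acts on the grade of nausea or vomiting, diarrhea, hypercalcemia or other unexpected toxicity.
- Section 8.4.1 sends serious adverse events to the Principal Investigator, from consent until 30 days after the last dose.

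**The concern.** The reason given in 4.2.10 is about taking the two drugs together, so it holds in the third cycle as much as on the first day. Treatment lasts six 28-day cycles and may run to 2 years in total for patients with a partial response or better. That leaves time for an indication for anticoagulation to arise.

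A site that followed the text exactly could record new outpatient warfarin, continue curcumin at 8 g/day and have no stated duty to tell the Principal Investigator. What is at stake is patient safety and consistent handling of such patients, not the efficacy analysis.

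**Working it through.** The plan gives no figure on this point to reproduce. The check is first a comparison of the text, then a rough size under stated assumptions.

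**1. Is there an on-study counterpart to 4.2.10?** Sections 6.1 to 6.3, 7.0, 8.1, 11.1 to 11.2 and Appendices E and F contain no rule naming therapeutic anticoagulants. Of the four drug types in 4.2.10 (heparin, low-molecular-weight heparin, warfarin, direct thrombin inhibitors), none is listed in Appendix E (CYP1A2 and CYP2A6) or Appendix F (CYP3A4).

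**2. Are other entry bars carried forward?**
- Pregnancy (4.2.4) becomes a named stopping reason in 6.3.
- Hypercalcemia (4.2.5.1) has its own table in 7.0, and a hold of vitamin D3 above 11 mg/dL in the vitamin D3 risk text of 8.1.
- Antiretrovirals (4.2.11) are partly carried: ten appear in Appendix F, and atazanavir is also in Appendix E.
- Anticoagulants are not carried, and nothing in the protocol explains the difference.

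**3. What do the existing safeguards catch?** Most adverse-event admissions are serious under 8.2.3 (exceptions include stays under 12 hours and pre-planned admissions), so anticoagulation started during one should come to the Principal Investigator's notice under 8.4.1. An outpatient start need not. Neither route says whether to hold curcumin.

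**4. How many patients?** From the documents: 29 evaluable patients and an enrolment maximum of 35 (3.2); 6 cycles of 28 days = 168 days (6.0); 2-year cap (6.0). Assumed: a start rate of 1% to 5% per year, every patient completing six cycles, and a Poisson count, so that P(at least one) = 1 − exp(−expected).
- Treatment time per patient: 168 / 365.25 = 0.460 years.
- 29 patients: 29 × 0.460 = 13.34 patient-years. Expected 0.133 to 0.667; P(at least one) 12% to 49%.
- 35 patients: 35 × 0.460 = 16.10 patient-years. Expected 0.161 to 0.805; P(at least one) 15% to 55%.
- 29 patients, 10% extending to 2 years (assumed): 13.34 + 0.10 × 29 × (2 − 0.460) = 17.8 patient-years. Expected 0.18 to 0.89.
- 29 patients, 30% extending (assumed): 13.34 + 0.30 × 29 × 1.540 = 26.74 patient-years. Expected 0.267 to 1.337; P(at least one) 23% to 74%; P(two or more) 3% to 39%.

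The 30% share is probably high. The 30% alternative in 14.2 is for an endpoint that counts biologic response, while extension requires a partial response or better.

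**5. Timing.** Accrual closed on 4/12/2016 (10.5). If the last first dose came within 30 days (assumed, after the screening window in 11.1.1), that is 5/12/2016. Two years later is 5/12/2018, which is 143 days before version 7 (10/2/2018).

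**The case against.** The strongest reply is that the protocol already handles this. Every drug is recorded. Section 6.3 gives three routes that a sensible investigator would use. An illness needing anticoagulation is likely to be an adverse event itself, since 8.2.1 does not require causality; the unexpected-toxicity table in 7.0 could then hold both agents at Grade 2 and stop them at Grade 3. All patients are registered through one institution, which limits variation in handling. The 6.1.1 sentence is a dosing instruction, not a waiver of a safety exclusion. The case is rare, and dosing had very likely ended before this version.

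Much of this stands, and it limits the point. It does not remove it. Recording triggers no action, 6.3 names no drug, and whether 7.0 covers an event unrelated to the study agents is unclear. For CYP agents, 6.2 does not leave matters to judgement but requires an alert; the 4.2.10 drugs, barred for an explicit safety reason, get none by name.

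Three stronger readings are tempting, and the documents do not support them.
- A reader might infer that the Principal Investigator would not hear of any such patient. Section 8.4.1 rules that out for most adverse-event admissions.
- A reader might infer that Appendices E and F are defective. They are organised by CYP enzyme, and leaving anticoagulants out is not an error in them.
- A reader might take the spacing of medication reviews as the size of the problem: 28 days between Day 1 visits, or 28 + 3 + 3 = 34 if the visit window applies at both ends. A named alert would not shorten that interval.

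**Conclusion.** The point holds as a limited safety gap. The reason for 4.2.10 applies throughout treatment, but no on-study rule carries it forward, and the exposed case is mainly an anticoagulant started as an outpatient. Probably at most about one patient would be affected. That rests on a start rate the documents do not give, and the figures are expectations, not limits: in the least favourable corner (5% per year, 30% extending) the expectation is 1.34.

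The documents do not show that the combination is harmful, only that its safety was not established, and nothing here shows that any patient was exposed. No efficacy result or decision rule changes. With accrual closed and therapy capped at 2 years, the correction matters mainly for reuse of the regimen.

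**What to change.** - **6.1.1:** add to the sentence on other medications an exception for the agents in 4.2.10.
- **6.2, alert:** extend the Principal Investigator alert by name to therapeutic heparin, low-molecular-weight heparin, warfarin and direct thrombin inhibitors.
- **6.2, action:** require curcumin to be held while one of these is given, with the patient going off protocol therapy if the Principal Investigator judges that anticoagulation will be long-term. This gives the hold an end without borrowing the two-week limit in 7.0, which belongs to the toxicity tables.
- **Optional, for this trial:** flag in the safety listing the adverse events that occurred on such a drug. Section 6.2 already collects the medication data.

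The cost is a few sentences and an occasional dose interruption or early discontinuation, in about the small numbers of patients shown above. No new data, sample-size change or error-rate change is involved.

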# 6.3 **Duration of Therapy**

In the absence of treatment delays due to adverse events, which are not generally expected, treatment may continue for 6 cycles [or can be extended for a total of 2 years if sustained a partial response (PR) or better] until one of the following criteria applies:

- Disease progression,
- Intercurrent illness that prevents further administration of treatment,
- The investigator considers it, for safety reasons, to be in the best interest of the patient.
- Unacceptable treatment related toxicity, NCI CTC AE version 4.0. Grade 3 or 4 that fails to recover to baseline or < Grade 3 in the absence of treatment within 4 weeks]
- General or specific changes in the patient's condition render the patient unacceptable for further treatment in the judgment of the investigator,
- Patient decision to withdraw from treatment (partial consent) or from the study (full consent),
- Pregnancy during the course of the study for a child-bearing participant
- Death

The date and reason for discontinuation must be documented. Every effort should be made to complete the appropriate assessments.

# 6.4 **Duration of Follow Up**

**30-Day Follow-Up**: Patients will be followed for toxicity for 30 days after treatment has been discontinued or until death, whichever occurs first.

**Long term Follow-Up**: Patients will be followed, every 3-6 months (as clinically indicated), for 2 years after discontinuation of study medications for long-term outcomes.

The clinical course of each event will be followed until resolution, stabilization, or until it has been determined that the study treatment or participation is not the cause.

Serious adverse events that are still ongoing at the end of the study period will necessitate follow-up to determine the final outcome. Any serious adverse event that occurs after the study period and is considered to be possibly related to the study treatment or study participation will be recorded and reported immediately.

# 7.0 DOSING DELAYS / DOSE MODIFICATIONS

As both agents are well-tolerated with no expected grade 3-4 toxicities, no dose modifications are planned for this study. No hematological toxicities are expected with either agent.

Event Name	Nausea and/or vomiting		
Grade of	Management/Next Management/Next		
Event	Dose for curcumin	Dose for vitamin D3	
≤ Grade 1	No change in dose	No change in dose	
	Hold until $\leq$ Grade 1.	Hold until $\leq$ Grade 1.	
Grade 2	Resume at same dose	Resume at same dose	
	level.	level.	
Grade 3	Off protocol therapy	Hold * until < Grade	
		Off protocol therapy	
Grade 4	Off protocol therapy	Off protocol therapy	
*Patients requiring a delay of >2 weeks should go off protocol therapy.			
Recommended management: anti-emetics.			

Event Name	Diarrhea	
Grade of	Management/Next	Management/Next
Event	Dose for curcumin	Dose for vitamin D3

≤ Grade 1	No change in dose	No change in dose	
	Hold until $\leq$ Grade 1.	Hold until $\leq$ Grade 1.	
Grade 2	Resume at same dose	Resume at same dose	
	level.	level.	
Grada 3	Decrease the dose to	Off protocol therapy	
Utaue 5	4 g PO daily		
Grade 4	Off protocol therapy	Off protocol therapy	
*Patients requiring a delay of >2 weeks should go off protocol therapy.			
Recommended management: Loperamide antidiarrheal therapy			
Dosage schedule: 4 mg at first onset, followed by 2 mg with each loose			
motion until diarrhea-free for 12 hours (maximum dosage: 16 mg/24			
hours)			
Adjunct anti-diarrheal therapy is permitted and should be recorded when			
used.			

Event Name	Hypercalcemia		
Grade of	Management/Next Management/Next		
Event	Dose for curcumin	Dose for vitamin D3	
$\leq$ Grade 1	No change in dose	No change in dose	
	Hold until $\leq$ Grade 1.	Hold until $\leq$ Grade 1.	
Grade 2	Resume at same dose	Resume at same dose	
	level.	level.	
Grade 3	Off protocol therapy	Off protocol therapy	
Grade 4	Off protocol therapy	Off protocol therapy	
*Patients requiring a delay of >2 weeks should go off protocol therapy.			
Recommended management: workup for hypercalcemia as per standard			
of care			

Event Name	Other Unexpected toxicity		
Grade of	Management/Next Management/Next		
Event	Dose for curcumin	Dose for vitamin D3	
≤Grade 1	No change in dose	No change in dose	
	Hold until $\leq$ Grade 1.	Hold until $\leq$ Grade 1.	
Grade 2	Resume at same dose	Resume at same dose	
	level.	level.	
Grade 3	Off protocol therapy	Off protocol therapy	
Grade 4	Off protocol therapy	Off protocol therapy	
*Patients requiring a delay of >2 weeks should go off protocol therapy.			
Recommended management: per standard of care			

**8.0** ADVERSE EVENTS: LIST AND REPORTING REQUIREMENTS The following is a list of AEs (Section 8.1) and the reporting requirements associated with observed AEs (Sections 8.3 and 8.4).

The clinical course of each event will be followed until resolution, stabilization, or until it has been determined that the study treatment or participation is not the cause.

Serious adverse events that are still ongoing at the end of the study period will necessitate follow-up to determine the final outcome. Any serious adverse event that occurs after the study period and is considered to be possibly related to the study treatment or study participation will be recorded and reported immediately.

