#### Amendment 5, v date 2/16/2015

**Protocol:** Quality of life assessments at baseline and at end of treatment added. Curcumin dose reduction adjusted to 4g daily with grade 3 diarrhea. **Consent:** Consent updated to include mandatory QOL assessments.

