#### 1.2.6.4 *Toxicity*

Toxicity or changes in body weight have not been seen in pre-clinical studies of long-term curcumin use (48) and (36). Little demonstrable toxicity is observed at *in vivo* doses of up to 5 g/kg (35). No significant toxicities have been reported from almost 40 clinical trials involving over 800 participants. Patients have tolerated up to 8 g oral curcumin daily for three months (45) and escalation beyond this, although safely achievable, was limited by the volume of capsules necessary to deliver the dose. Side-effects are dose-related and typically gastrointestinal in origin, including loose stools, bloating, reflux and discomfort. Dose reduction usually leads to improvement. Trials consistently report curcumin has no effect on biochemical and haematological parameters during administration. There have been anecdotal reports of transient rises in liver enzymes although causality is unclear.

CASE **5913** 

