# 8.1 Adverse Events and Potential Risks

# 8.1.1 Curcumin

The most common side effects (occurs in more than 10 of 100 people) reported in clinical trials are:

- mild nausea
- vomiting
- diarrhea
- reflux
- bloating

All resolved with discontinuation of therapy.

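### Section 7.0 holds curcumin for Grade 2 diarrhea but only halves the dose, with no hold, for Grade 3

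*Combined protocol and SAP*

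**What the plan says.** Planned curcumin dosing is 8 g daily without breaks (section 6.1.1). Section 7.0 gives four toxicity tables, each with one column for curcumin and one for vitamin D3.

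In the diarrhea table:

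- **Grade 2:** both agents are interrupted ("Hold until $\leq$ Grade 1") and then resumed at the same dose level.
- **Grade 3:** the curcumin cell begins "Decrease the dose to" and sets 4 g by mouth daily. It contains nothing else. Vitamin D3 goes off protocol therapy.
- **Grade 4:** both agents go off protocol therapy.
- **Footnote:** "Patients requiring a delay of >2 weeks should go off protocol therapy". Loperamide is recommended.

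The summary of changes shows where the reduction came from: "Curcumin dose reduction adjusted to 4g daily with grade 3 diarrhea" (Amendment 5, dated 2/16/2015).

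On the link between curcumin and diarrhea, section 1.2.6.4 describes dose-related gastrointestinal effects, including loose stools, and adds "Dose reduction usually leads to improvement". Section 8.1.1 includes diarrhea in the list introduced by "The most common side effects (occurs in more than 10 of 100 people) reported in clinical trials are" and closes that list with "All resolved with discontinuation of therapy".

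Section 6.3 ends treatment for unacceptable related toxicity, described as "Grade 3 or 4 that fails to recover to baseline or < Grade 3 in the absence of treatment within 4 weeks".

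**The concern.** A severity-graded rule should become no more lenient as the event gets worse. Here it does, for the agent the protocol itself associates with the event: curcumin is withheld at Grade 2 and given at half dose at Grade 3. An investigator following the cell literally would keep dosing a patient with severe diarrhea who would have been taken off the drug, at least temporarily, had the diarrhea been moderate.

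There is also a mismatch between sections. The recovery test in section 6.3 is defined off treatment, so it presupposes that dosing has been paused. With the Grade 3 diarrhea cell as written, curcumin has not been paused and the test has no starting point.

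What is at stake is patient safety and an unambiguous instruction to sites. It is not the statistical operating characteristics of the trial.

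**Working it through.** The plan gives no figure to reproduce here. The check is a cell-by-cell comparison.

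**1. Is the row really Grade 3?** The row label is damaged in the text available for this review. The row sits between Grades 2 and 4, and Amendment 5 ties the 4 g dose to Grade 3 diarrhea. Both identify it as Grade 3.

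**2. Action on curcumin in every cell for Grades 2 to 4 (section 7.0):**

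| Table | Grade 2 | Grade 3 | Grade 4 |
|---|---|---|---|
| Nausea/vomiting | hold | stop | stop |
| Diarrhea | hold | **4 g daily, no hold** | stop |
| Hypercalcemia | hold | stop | stop |
| Other unexpected toxicity | hold | stop | stop |

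Cells: 4 tables x 3 grades = 12. Cells that hold or stop curcumin: 11. Exception: 12 - 11 = 1, Grade 3 diarrhea.

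**3. Daily curcumin while diarrhea lasts, read literally:** Grade 1 or less, 8 g; Grade 2, 0 g; Grade 3, 4 g (4/8 = 50% of the planned dose); Grade 4, 0 g. The sequence 8, 0, 4, 0 does not fall steadily with severity.

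**4. Does other text supply the hold?**

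- *Column header.* It covers both management and the next dose, so 4 g might be meant as the dose after recovery. But the Grade 2 cell under the same header writes out its hold and its resumption. Silence in the next row cannot safely be read as the same instruction.
- *Two-week footnote.* It acts on a patient who needs a delay. The Grade 3 curcumin cell orders none, so nothing starts that clock.
- *Section 6.3.* It measures recovery without treatment but does not itself order an interruption.
- *Amendment 5.* It explains the choice of 4 g. It does not say that dosing should continue through the event.

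**5. Does the correction still affect treatment?** Section 10.5 dates closure of accrual to 4/12/2016. Six cycles are 6 x 28 = 168 days, which from that date gives 9/27/2016. The extension to 2 years in total (section 6.0) gives 4/12/2018. Allowing 30 days from screening to first dose (section 11.1.1) moves these to about 10/27/2016 and 5/12/2018, both before version 7 of 10/2/2018. Section 10.4.2 speaks of a 2-year continuation phase. If that were counted after cycle 6, the latest date would be about 10/27/2018. Completion before version 7 is therefore probable, not certain.

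**The case against.** The strongest reply is that the reduction was deliberate and has a stated basis. Amendment 5 set it, and section 1.2.6.4 says lowering the dose usually helps. That stands for the 4 g dose, which this point leaves alone. It does not explain why dosing continues through Grade 3 when Grade 2 requires a pause.

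A second reply is that patients are protected anyway: loperamide is recommended, and section 6.3 lets the investigator stop for safety. This lowers the risk and stands to that extent. Neither puts a hold in the row, and a dose table exists so that such decisions do not rest on discretion alone.

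A third reply is that a change now would probably alter no patient's treatment. That is fair, and it limits the urgency.

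A reader might go further than the documents allow in four ways:

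- **That the vitamin D3 cell in this row is unclear.** It is legible, it stands in the vitamin D3 column, and curcumin continues beside it. Only an agent-specific stop fits the row, so the matter is one of wording.
- **That the excess exposure can be capped by multiplying 4 g by the footnote's two weeks.** The footnote limits a delay, and this cell orders none, so the product bounds nothing.
- **That the rate in section 8.1.1 shows how many patients are affected.** It covers diarrhea of any grade. The protocol gives no Grade 3 rate, and section 7.0 expects no Grade 3-4 toxicity.
- **That a patient improving from Grade 3 to Grade 2 must then be held.** The protocol does not say whether a resolving event is managed again at its new grade.

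**Conclusion.** The point holds for the curcumin cell. As written, Grade 3 diarrhea is managed less strictly than Grade 2 for the agent linked to it, in 1 of 12 comparable cells, and section 6.3 assumes an interruption that the cell does not give. Per affected patient the difference is 4 g daily during Grade 3 against 0 g during Grade 2; its duration and frequency are unknown.

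This is a safety and consistency correction of modest size. No effect on sample size, type I error or power is claimed. The conclusion rests on reading the cell literally and on the row being Grade 3. Its practical weight for this trial is limited because dosing was probably complete before version 7; the main value is a correct rule in the current text and in any later protocol that reuses it.

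**What to change.** Change the Grade 3 curcumin cell of the diarrhea table to: *Hold until Grade 1 or less (off protocol therapy if the delay exceeds 2 weeks), then resume at 4 g daily.* The recovery level matches the Grade 2 row, the two-week limit is the table's own, and the Amendment 5 dose is kept.

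As a minor clarification, word the Grade 3 vitamin D3 cell as: *Stop vitamin D3 permanently; curcumin continues as in its own column.* This keeps the stop already there and says which agent it applies to.

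The cost is two table cells, with no new patients, procedures or case report fields. The downside is a short interruption in affected patients, and permanent discontinuation in those whose delay exceeds 2 weeks. Under section 3.3, a patient who stops before completing two cycles is not evaluable for response and may be replaced.
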